7.3 Subject Population(s) for Analysis

All patients who completed the study will be included in the final analysis. Additionally, we will note patient withdrawal rates as well as the reasons for patient withdrawal.

8 Safety and Adverse Events

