Study Product, Dose, Route, Regimen	This study will evaluate the efficacy of adductor canal pain catheters following total knee arthroplasty, using either an intermittent bolus or continuous infusion compared to a single-shot adductor canal block.
Duration of Administration	4 days
Reference therapy	Single-shot adductor canal block
Statistical Methodology	Statistical analysis will be performed on the basis of the intention to treat principle. Comparisons between treatment groups will be made using Wilcoxon rank sum test or Fisher's exact test.

1 Introduction

This document is a protocol for a human research study. This study will be carried out in accordance with the applicable United States government regulations and Mayo Clinic research policies and procedures.

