surgery and bolused with 10 mL of 0.5% ropivacaine. The pumps will be loaded with saline (single shot adductor canal group), or ropivacaine 0.2%, dispersed in either a continuous infusion (6 mL/hr) or pulsed intermittent bolus (8 mL every 2 hours). All groups will have a patient demand dose of 6 mL/hr for anterior knee pain. The medication for the adductor catheter will be dispersed to the anesthesia team by the research pharmacy. The anesthesia team will place the catheter under ultrasound guidance in the recovery room. They will adjust the delivery mode based on patient randomization. The anesthesia team will record the serial number of the pump at the time of placement.

Questionnaires will be sent electronically to the patient. Results will be collected daily for 14 days postoperatively, followed by weekly questionnaires until they discontinue narcotic medications. Additional questionnaires will be collected at 30 and 60 days postoperatively in order to record pain and KOOS Jr. scores. The questionnaires will be sent in the morning; if a patient fails to fill out the questionnaire by the afternoon, a member of the research team will contact the patient to obtain the data. The questionnaires will document numerical rating scale (NRS) pain scores, information on symptoms of nausea, vomiting, and constipation, and will inquire if the patient is still consuming narcotic medication.

Following discontinuation of the catheter the patient will remove and return the device to the supplier. The supplier will then provide the rate of on-demand usage to the research team by way of device serial number. This information will be stored in Redcap.

Subjects will be withdrawn prior to completion if they ask to be removed from the study. They may also be withdrawn from the study if they have a serious adverse reaction to one of the prescribed medications. Finally, subjects may be withdrawn at the discretion of the treating physician. If subjects are withdrawn early their last recorded pain score will be carried forward until study conclusion in order to perform intention to treat analysis. The study will continue to ascertain duration of narcotic use with weekly questionnaires, until the patient has stopped the medication.

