3.4 Primary Study Endpoints

The primary endpoint will be pain scores, calculated by the Numerical Rating Scale. This score will be collected daily during the hospital examination and by online or phone surveys after discharge. We will calculate the mean difference in recorded pain scores between cohorts. We hypothesize that the intermittent bolus infusion cohort will report improved pain scores compared to continuous infusion catheters.

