7.2 Statistical Methods

Descriptive and Inferential Statistics

Continuous variables will be summarized with the sample mean, median, standard deviation, minimum, 25th percentile, 75th percentile, and maximum. Categorical variables will be summarized with number and percentage of patients. All analysis will be performed on the basis of the intention-to-treat principle. Comparisons of endpoints between the three treatment arms will be made using a Wilcoxon rank sum test (continuous or ordinal endpoints) or Fisher's exact test (categorical endpoints). Missing data will be imputed using either the last observation carried forward method, a regression-based approach, or another method, depending on the extent of missing data. In order to adjust for the three pair-wise comparisons between treatment groups that will be made for each endpoint, we will utilize a Bonferroni correction for multiple testing, after which p-values of < 0.0167 will be considered as statistically significant. All statistical tests will be two-sided.

Primary Hypothesis:

We hypothesize that the intermittent bolus infusion cohort will report improved pain scores compared to continuous infusion catheters and placebo cohorts.

Secondary Hypothesis:

We hypothesize that the intermittent bolus cohort will require fewer doses of patient-administered medication and will use narcotic medication for a shorter duration when compared to the continuous infusion and placebo groups.

Interim Analysis

We will evaluate the first twenty patients. If 50% of the patients are withdrawn from the study for poor pain control or serious adverse reactions to the study medication, then we will close the study early.

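### Section 7.3 puts completers in the final analysis, against the intention-to-treat analysis required elsewhere; because pain triggers withdrawal, following 7.3 would select on the primary endpoint

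*Combined protocol and SAP*

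**What the plan says.** Three places set the analysis principle. The Study Summary says "Statistical analysis will be performed on the basis of the intention to treat principle". Section 7.2 says "All analysis will be performed on the basis of the intention-to-treat principle". Section 3 says that for subjects withdrawn early "their last recorded pain score will be carried forward until study conclusion in order to perform intention to treat analysis".

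Section 7.3, the section headed as the analysis population, reads differently: "All patients who completed the study will be included in the final analysis". For everyone else it adds that "we will note patient withdrawal rates as well as the reasons for patient withdrawal".

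Withdrawal is tied to pain. Section 3.6 withdraws patients who report uncontrolled pain, and Section 8.5 those whose pain becomes intolerable without more narcotic. Sections 4.4.1 and 8.5 also withdraw patients for unmet protocol requirements or questionnaires not completed. The primary endpoint (Section 3.4) is the NRS pain score.

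On missing data, Section 3 specifies LOCF for pain after withdrawal. Section 7.2 has missing values "imputed using either the last observation carried forward method, a regression-based approach, or another method, depending on the extent of missing data". On follow-up after withdrawal, Section 3 says "The study will continue to ascertain duration of narcotic use with weekly questionnaires, until the patient has stopped the medication", whereas Section 4.4.2 mentions only data gathered up to withdrawal.

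**The concern.** Two analysts could each follow this plan faithfully and analyse different patients. One would keep all 84 randomised patients and fill in scores after withdrawal. The other would take Section 7.3 as the population definition and report withdrawn patients as a count with reasons.

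The choice matters because completion is not independent of the outcome. If high pain leads to withdrawal, more patients leave the arm with worse pain, and those who remain look more alike across arms than the randomised groups were. The comparison loses the protection of randomisation and a true difference shrinks.

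The trial is a pilot sized for feasibility. It nevertheless tests each pairwise comparison at p < 0.0167 (Section 7.2), and Section 7.1 says its data will feed the power analysis of a larger study, so a shrunken difference could carry into that design.

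Within the intention-to-treat route, a method chosen after the extent of missing data is known leaves room for a choice made with results in view.

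**Working it through.** **1. The passages side by side.** If Section 7.3 governs, withdrawn patients are not in the final analysis, and the carry-forward rule in Section 3 has nobody to act on. If Section 3 and Section 7.2 govern, withdrawn patients are in, and Section 7.3 is incomplete. Both cannot stand as written. The documents give no power, SD, effect size or withdrawal rate, so there is no stated figure to reproduce; the stated counts (3 × 28 = 84) and threshold (0.05/3 = 0.0167) are consistent.

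**2. Direction of the completer effect, by hand.** Assume normal pain with SD s = 2, means 4 (worse arm) and 3 (better arm), and withdrawal above c = 6. The completer mean is m − s·φ(a)/Φ(a), with a = (c − m)/s.

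- Worse arm: a = 1.0; 4 − 2 × 0.2420/0.8413 = 3.42; withdrawn 15.9%.
- Better arm: a = 1.5; 3 − 2 × 0.1295/0.9332 = 2.72; withdrawn 6.7%.
- Completer difference: 3.42 − 2.72 = 0.70, against a true 1.0.

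With c = 8 (2.3% and 0.6% withdrawn) the completer difference is 0.92. Over SD 2-2.5, true difference 0.5-1.5 and c = 6-8, completers keep 60-94% of the truth.

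**3. Daily scores.** All inputs are assumed: rounded 0-10 NRS on days 1-14, mean 5 or 6 on day 1 falling linearly to 2.5 on day 14, between-patient SD 1.5, day-to-day SD 1.2, benefit 1.0 on days 1-4 only, and withdrawal after two consecutive days at or above 8 or 9. This withdraws 2-15% in the worse arm and 1-8% in the better arm.

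| Mean difference | True | Completers | LOCF |
|---|---|---|---|
| Days 1-4 | 0.98-0.99 | 0.80-0.95 | 0.99-1.03 |
| Days 1-14 | 0.27-0.28 | 0.12-0.25 | 0.30-0.48 |

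With a one-day trigger (8-38% and 5-25% withdrawn), completers give 0.67-0.87 on days 1-4, and LOCF gives 0.41-0.77 over 14 days. An exponential fall between the same endpoints (rate 0.3 per day) takes the 14-day LOCF figure above 0.8, so none of these ranges is a limit.

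**4. Against sampling error.** The standard error of a days 1-4 difference with full data is √[2 × (1.5² + 1.2²/4)/28] = √(2 × 2.61/28) = 0.43. The largest completer shift in the table for days 1-4 is 0.99 − 0.80 = 0.19.

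**5. When there is no distortion.** With no benefit and equal withdrawal in the arms, all routes agree within 0.01.

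**6. Why LOCF needs thought.** Pain falls over the two weeks, so a high score at a pain-triggered withdrawal, carried forward, overstates that patient's later pain. If such withdrawals are commoner in the worse arm, later differences are inflated. The direction is not guaranteed: adding 20% non-pain withdrawal in the better arm only gives a 14-day LOCF difference of 0.25-0.40, which reaches below the true 0.27-0.28.

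**The case against.** The best defence is that Section 7.3 says completers are included and excludes nobody in words. Three other statements require intention-to-treat, and a reading that empties the Section 3 rule of content is a poor one. It is right that the documents do not support saying that 7.3 expressly restricts the analysis to completers. What stands is that a section on analysis populations names one group, gives the rest a count, and never mentions the intention-to-treat set.

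It is also fair that Section 1.5 and Section 3.1 provide rescue and standard opioids, so pain withdrawal may be rare. However, the interim rule in Section 7.2, which closes the study if half of the first twenty are withdrawn for poor pain control or serious adverse reactions, shows that it was foreseen.

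A reader might infer more on missing data than the text bears:

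- The handling of pain scores after withdrawal is not left wholly open. Section 3 fixes LOCF, and Section 7.2 can be read as covering other gaps. The remaining criticism is that 7.2 does not say so and lets the amount of missing data decide.
- The endpoint wording "We will calculate the mean difference in recorded pain scores between cohorts" is ordinary language for collected scores, not a further missing-data rule.
- Section 4.4.2 does not forbid later data. It is merely silent where Section 3 is explicit.

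Finally, preferring another method to LOCF as primary is partly a matter of judgement. On the days 1-4 mean, LOCF barely moves the simulated Wilcoxon rejection rate (40-43%, against 40-44% with full data); completers give 21-42% across the two triggers.

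**Conclusion.** The point holds. Section 7.3 conflicts with the intention-to-treat analysis stated in the Study Summary, Section 3 and Section 7.2. Following it would select patients on the primary endpoint and move a true difference toward zero.

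This rests on the wording and on the pain-related withdrawal provisions, not on the simulated sizes. Under the assumed inputs with 2-15% pain withdrawal in the worse arm, a true days 1-4 difference of about 0.98 falls to about 0.8-0.95. That shift is below the standard error of 0.43 at 28 per arm. The sizes are scenarios: the real withdrawal rate, pain SD and shape of recovery are unknown, and the effect of alternative medication after withdrawal was not modelled. It would be wrong to read them as bounds, or to infer a false difference between arms with equal pain and equal withdrawal.

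The missing-data point is secondary. One rule is fixed in Section 3 and a wider choice is left open in Section 7.2, and the two should agree.

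**What to change.** 1. Replace Section 7.3 with: *All randomised patients will be analysed in the arm to which they were assigned; an analysis of patients who completed follow-up may be reported as a sensitivity analysis.*
2. Before unblinding, name one primary missing-data method in Section 7.2 and make Section 3 agree with it. The regression-based approach that 7.2 already allows is one candidate, in a form that can be fitted with 28 per arm. Report LOCF or another method as a sensitivity analysis.
3. Align Section 4.4.2 with Section 3, so that the existing questionnaires continue after withdrawal unless consent is withdrawn.
4. Reconcile the withdrawal provisions in Sections 3, 3.6, 4.4.1 and 8.5 with one another. No clinical or unblinding rule is proposed here.

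The cost is protocol wording, a little more analysis, and a little more follow-up through questionnaires and telephone back-up that already exist. No extra visits are needed, and the sample size stays at 84.

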8.1 Definitions

Unanticipated Problems Involving Risk to Subjects or Others (UPIRTSO)

Any unanticipated problem or adverse event that meets the following three criteria:

- Serious: Serious problems or events that results in significant harm, (which may be physical, psychological, financial, social, economic, or legal) or increased risk for the subject or others (including individuals who are not research subjects). These include: (1) death; (2) life threatening adverse experience; (3) hospitalization - inpatient, new, or prolonged; (4) disability/incapacity - persistent or significant; (5) birth defect/anomaly; (6) breach of confidentiality and (7) other problems, events, or new information (i.e. publications, interim findings, product labeling change) that in the opinion of the local investigator may adversely affect the rights, safety, or welfare of the subjects or others, or substantially compromise the research data, **AND**
- Unanticipated: (i.e. unexpected) problems or events are those that are not already described as potential risks in the protocol, consent document, not listed in the Investigator's Brochure, or not part of an underlying disease. A problem or event is "unanticipated" when it was unforeseeable at the time of its occurrence. A problem or event is "unanticipated" when it occurs at an increased frequency or at an increased severity than expected, **AND**
- Related: A problem or event is "related" if it is possibly related to the research procedures.

Adverse Event

An untoward or undesirable experience associated with the use of a medical product (i.e. drug, device, biologic) in a patient or research subject.

Serious Adverse Event

Adverse events are classified as serious or non-serious. Serious problems/events can be well defined and include;

- death
- life threatening adverse experience
- hospitalization
- inpatient, new, or prolonged; disability/incapacity
- persistent or significant disability or incapacity
- birth defect/anomaly

and/or per protocol may be problems/events that in the opinion of the sponsor-investigator may have adversely affected the rights, safety, or welfare of the subjects or others, or substantially compromised the research data.

All adverse events that do not meet any of the criteria for serious, should be regarded as **non-serious adverse events**.

Adverse Event Reporting Period

For this study the follow-up period is defined as 2 weeks following the surgical procedure.

Preexisting Condition

A preexisting condition is one that is present at the start of the study. A preexisting condition should be recorded as an adverse event if the frequency, intensity, or the character of the condition worsens during the study period.

General Physical Examination Findings

At screening, any clinically significant abnormality should be recorded as a preexisting condition. At the end of the study, any new clinically significant findings/abnormalities that meet the definition of an adverse event must also be recorded and documented as an adverse event.

Post-study Adverse Event

All unresolved adverse events should be followed by the sponsor-investigator until the events are resolved, the subject is lost to follow-up, or the adverse event is otherwise explained. At the last scheduled visit, the sponsor-investigator should instruct each subject to report, to the sponsor-investigator, any subsequent event(s) that the subject, or the subject's personal physician, believes might reasonably be related to participation in this study.

Abnormal Laboratory Values

A clinical laboratory abnormality should be documented as an adverse event if the post-treatment liver or renal function labs demonstrate a significant elevation from the recorded baseline value.

Hospitalization, Prolonged Hospitalization or Surgery

Any adverse event that results in hospitalization or prolonged hospitalization should be documented and reported as a serious adverse event unless specifically instructed otherwise in this protocol. Any condition responsible for surgery should be documented as an adverse event if the condition meets the criteria for an adverse event.

Neither the condition, hospitalization, prolonged hospitalization, nor surgery are reported as an adverse event in the following circumstances: Elective surgical procedures.

8.2 Recording of Adverse Events

At each contact with the subject, the study team must seek information on adverse events by specific questioning and, as appropriate, by examination. Information on all adverse events should be recorded immediately in the source document, and also in the appropriate adverse event section of the case report form (CRF). All clearly related signs, symptoms, and abnormal diagnostic, laboratory or procedure results should be recorded in the source document.

All adverse events occurring during the study period must be recorded. The clinical course of each event should be followed until resolution, stabilization, or until it has been ultimately determined that the study treatment or participation is not the probable cause. Serious adverse events that are still ongoing at the end of the study period must be followed up, to determine the final outcome. Any serious adverse event that occurs during the Adverse Event Reporting Period and is considered to be at least possibly related to the study treatment or study participation should be recorded and reported immediately.

8.3 Reporting of Serious Adverse Events and Unanticipated Problems

When an adverse event has been identified, the study team will take appropriated action necessary to protect the study participant and then complete the Study Adverse Event Worksheet and log. The sponsor-investigator will evaluate the event and determine the necessary follow-up and reporting required.

8.3.1 Sponsor-Investigator reporting: notifying the Mayo IRB

The sponsor-investigator will report to the Mayo IRB any UPIRTSOs and NonUPIRTSOs according to the Mayo IRB Policy and Procedures.

8.3.2 Sponsor-Investigator reporting: Notifying the FDA

Not applicable.

8.4 Unmasking/Unblinding Procedures

If patients are withdrawn early from the study they will be unblinded at that time.

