3.5 Secondary Study Endpoints

The secondary endpoints will be the amount of medication administered via the patient-controlled function on the adductor catheter as well as duration of narcotic use required in each cohort. We hypothesize that the intermittent bolus cohort will require fewer doses of patient-administered medication and will use narcotic medication for a shorter duration when compared to the continuous infusion and placebo groups.

We will additionally calculate the overall morphine equivalents used in each cohort during their hospitalization, and dividing this by the total number of post-surgical hospitalization hours in order to normalize the data.

Nausea and vomiting will be recorded daily using the postoperative nausea and vomiting scale and compared between groups. Presence of constipation will be a subjective rating by the patient that is also recorded daily. We will compare the post-surgery length of hospitalization between groups. Finally, we will compare patient-reported outcomes using the KOOS Jr. questionnaire.

We hypothesize that the intermittent bolus cohort will use less narcotic mediation and will therefore have lower rates of constipation, nausea and vomiting. Furthermore, we believe this cohort will demonstrate equivalent lengths of stay and patient-reported outcomes as compared to the comparison groups.

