3.7 Identification of Source Data

The following source data will be directly recorded on the Case Report Form (CRF) at the pre-op visit and inputted into REDcap, a password protected database.

- Name
- Medical Record Number
- Email address
- Date of Birth, Age
- Gender
- Race
- Weight (lbs), Height (In), BMI
- Previous surgeries? (yes, no)
- Are you taking Nsaids? (yes, no)
- Previous injections (yes, no)
- Baseline NRS score
- Laterality of surgery
- KOOS Jr. Questionnaire
- Device serial number

The following source data will be recorded daily for two weeks using an online questionnaire recorded into REDcap, and continued weekly until discontinuation of narcotic medication. This data will again be collected at 30 and 60 days following the date of surgery.

- Name
- Medical Record Number
- Date of Birth
- How long has it been since your operation? (Less than 1 month, 1-2 months, Greater than 2 months)
- Are you using narcotic medication? (yes/no)
 - What was the date you last consumed narcotic medication? (if no to previous answer)
- How would you rate the pain you have been experiencing? (0-10)

- Have you been experiencing constipation over the past 24 hours? (yes, no)
- Have you been vomiting or had dry-retching over the past 24 hours? (once, twice, three or more times, no)
- Have you been experiencing a feeling of nausea (an unsettled feeling in the stomach and slight urge to vomit) over the past 24 hours? (yes, no)
- KOOS Jr. Questionnaire (only recorded during 1 month and 2 month questionnaires)
- Rate of on-demand catheter use (recorded at final survey only)

4 Subject Selection Enrollment and Withdrawal

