5.6 Prior and Concomitant Therapy

If a patient has taken a narcotic medication (schedule II) in the 3 months leading up to surgery they will be excluded from the study. Patients may request and be provided refills for narcotic medication at the discretion of the treating surgeon.

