8.5 Stopping Rules

Subjects will be withdrawn from the study if they have a serious adverse reaction to any of the study drugs. Additionally, if patients are unable to complete the follow-up questionnaires they will be withdrawn. If patient's pain increases during the study period that is not tolerable without additional narcotic medication they will be withdrawn. Finally, we will withdraw patients from the study that no longer wish to participate.

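### Section 8.4 unblinds every patient who is withdrawn, while self-reported narcotic duration (Aim 3) is still being collected from them

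*Combined protocol and SAP*

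**What the plan says.** Section 8.4 is one sentence: "If patients are withdrawn early from the study they will be unblinded at that time". It sets no limit by reason or need, does not say who besides the patient is told, and asks for no record of the event.

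Two sentences at the end of Section 3 (Study Design) deal with patients who leave early. On pain: "If subjects are withdrawn early their last recorded pain score will be carried forward until study conclusion in order to perform intention to treat analysis". On narcotics, directly afterwards: "The study will continue to ascertain duration of narcotic use with weekly questionnaires, until the patient has stopped the medication".

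Narcotic duration is a secondary endpoint. Section 3.5 lists it: "as well as duration of narcotic use required in each cohort". Section 3.7 shows that it comes from the patient, through a yes/no item on current use and the question "What was the date you last consumed narcotic medication". The surgeon can also influence it, because Section 5.6 states: "Patients may request and be provided refills for narcotic medication at the discretion of the treating surgeon".

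Section 8.5 lists the grounds for withdrawal. One concerns pain and narcotic need: "If patient's pain increases during the study period that is not tolerable without additional narcotic medication they will be withdrawn". Another is safety: "Subjects will be withdrawn from the study if they have a serious adverse reaction to any of the study drugs". The remaining two are inability to complete the questionnaires and the patient's wish to leave. Section 4.4.1 adds failure to meet protocol requirements and the physician's discretion.

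Section 5.8 otherwise keeps the patient and the surgical team blinded to drug and dosing mode.

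**The concern.** Blinding protects a self-reported outcome only while the reporter does not know the arm. Here the reporter is told the arm at withdrawal, and the outcome may still be open: the patient may go on taking narcotics for weeks and go on answering questions about them. Knowing that the pump held saline, or held ropivacaine in a given mode, can change what the patient reports and whether the patient asks for a refill.

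The patients concerned are not a random sample. One ground for withdrawal is pain that cannot be tolerated without more narcotic, which is closely tied to the endpoint itself. Unblinding is therefore concentrated among patients whose narcotic duration is likely to matter most to the comparison.

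For withdrawal at the patient's request or for missed questionnaires, the documents give no reason why anyone needs the assignment, so blinding is given up there for no stated purpose. Section 7.1 intends the results to inform the power calculation for a larger study, so a distorted estimate could carry forward.

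**Working it through.** The plan states no figure for this point: no withdrawal rate and no assumption about narcotic duration. The check is a comparison of sections, then a bound, then an illustration on assumed inputs.

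**1. Is the outcome collected after unblinding?**
- Section 8.4: unblinding happens at withdrawal, for all reasons.
- Section 3: narcotic duration is followed weekly until the drug is stopped, stated immediately after the rule for early withdrawals.
- Section 4.4.2: data from before withdrawal will be collected. It does not say that collection then ends, so it does not cancel Section 3, but the two do not match.
- Section 7.2: all analysis is by intention to treat.
- Section 7.3: the final analysis includes patients who completed the study.

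Under Sections 3 and 7.2, unblinded reports enter the Aim 3 analysis. Under a literal Section 7.3 they might not, but then a group selected on pain and narcotic need is dropped, against Section 7.2. The plan does not settle which applies.

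**2. Is the primary endpoint reached by this route?** No. Section 3 carries the last pain score forward, so no new score is taken after unblinding.

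**3. How many patients?** The sample size reproduces: 3 × 28 = 84. With an assumed share withdrawn:
- 10%: 0.10 × 84 = 8.4, about 8 patients
- 25%: 0.25 × 84 = 21 patients

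These are upper bounds at each assumed rate. A withdrawn patient who stops answering, or had already stopped narcotics, contributes no unblinded duration. The interim rule in Section 7.2 (closure at 50% of the first twenty, 0.50 × 20 = 10 patients) is a closing threshold, not an expected rate.

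**4. How much could it matter?** Illustration only; every input except the arm size, test and alpha is assumed.
- From the plan: 28 per arm, Wilcoxon rank sum, two-sided alpha 0.05/3 = 0.0167.
- Assumed: no true arm difference; log-normal duration with median 14 days and log-SD 0.8; withdrawals at random; each withdrawn patient's duration multiplied by a factor above 1 in one arm and below 1 in the other.
- 10,000 runs per setting. Simulation standard error at the nominal level: √(0.0167 × 0.9833 / 10,000) ≈ 0.0013.

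False-positive rate for one pairwise comparison:

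| Withdrawn per arm | No shift | ×1.25 / ×0.8 | ×1.5 / ×0.67 | ×2 / ×0.5 |
|---|---|---|---|---|
| 10% | 0.016 | 0.017 | 0.023 | 0.034 |
| 20% | 0.015 | 0.024 | 0.041 | 0.095 |
| 30% | 0.015 | 0.034 | 0.083 | 0.233 |

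The simulated mean differences agree with hand calculation. The log-normal mean is 14 × exp(0.8²/2) ≈ 19.3 days. At 20% withdrawn with ×1.25 / ×0.8, the expected difference is 0.20 × (1.25 − 0.80) × 19.3 ≈ 1.7 days; the simulation gave 1.75.

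At 10% withdrawn the mild shift cannot be told apart from the nominal level, and even the largest shift only doubles it. At 20% to 30% the inflation is material if the shifts are large. If both arms had the same withdrawal rate and the same shift, their distributions would be identical under the null and there would be no inflation. The problem therefore needs a response to unblinding, or a withdrawal rate, that differs by arm.

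**The case against.** The strongest reply is that the unblinded data may never be used. Section 4.4.2 speaks only of data before withdrawal, and Section 7.3 analyses completers. This stands as a reason for not treating the bias as certain. It does not remove the point: Section 3 states the continued collection in plain terms, and a completers-only analysis would contradict Section 7.2 and exclude an outcome-selected group.

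A second reply is that patients who ask to leave or cannot manage the questionnaires are the least likely to keep reporting. Those withdrawn for pain or a serious reaction may be unblinded even under a narrower rule. This also stands in part, and it limits how much of the exposure a rewrite of Section 8.4 alone would remove. It is one reason to add a sensitivity analysis.

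Three stronger readings are tempting, and the documents do not support them.
- **The surgeon learns the arm.** A reader might infer this and conclude that discretionary refills are affected. Section 8.4 refers to the patients, and Section 5.8 keeps the surgical team blinded. The plan is silent on whether the surgeon or survey staff are told at withdrawal; if they are, the refill route in Section 5.6 opens as well.
- **The bias favours the active arms.** This needs more pain withdrawals on saline and longer reported use once saline is known. Both are plausible, but neither is shown. Withdrawn patients in the active arms are unblinded too, and the argument does not apply to intermittent bolus against continuous infusion, where both pumps hold ropivacaine.
- **The trial's main result is compromised.** The primary pain score is carried forward and is not measured after unblinding. Narcotic duration is one of several secondary endpoints, in a study sized for feasibility.

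**Conclusion.** The point holds in limited form. The plan unblinds all early withdrawals without regard to need and, in Section 3, continues to collect a self-reported secondary endpoint from the same patients. Aim 3 can therefore be measured unblinded in a subgroup selected partly on pain and narcotic need, contrary to the blinding set out in Section 5.8. This follows from the text and needs no assumption about numbers.

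Size and direction cannot be derived from the documents. On an assumed 10% to 25% withdrawn, no more than 8 to 21 of 84 patients are involved. In the illustration, which assumes opposite shifts in two arms, the effect on the error rate is small at 10% withdrawn and can be material at 20% to 30%. The reason to change the rule is that it creates an avoidable risk of bias and is cheap to correct, not that a bias of known size has been shown.

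**What to change.** **Section 8.4.** State that withdrawal alone does not unblind. The code is broken only when the assignment is needed to manage the patient. State who then learns it, and record the date and reason. In all other cases the patient, surgical team and survey staff stay blinded until database lock.

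**Sections 3, 4.4.2, 7.2 and 7.3.** Make these agree on whether narcotic duration is collected after withdrawal and whether it is analysed under intention to treat.

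**Section 7.2.** Add a sensitivity analysis of narcotic duration for patients unblinded before their narcotic stop date. For example, censor these patients at the date of unblinding, or repeat the comparison over a plausible range of shifts in their durations. Report the number unblinded by arm and reason.

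**Cost.** One paragraph in Section 8.4, short edits to the other sections, one extra field for unblinding date and reason, and a small additional analysis. The research pharmacy already carries out the randomization. The drawback is that some patients learn their arm later.
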